2.5.1 Study design for non-pregnant cisgender women

This is an open-label, randomized, three-arm, directly observed therapy, pharmacologic study. HIV-uninfected non-pregnant cisgender women at low risk for HIV will be randomly assigned to 1 of 3 dosing frequencies of DOT TDF/FTC PrEP (**Figure 4**): 2, 4, or 7 doses per week to help differentiate poor and modest from perfect dosing (**Figure 4**).

Figure 4: Schema for directly observed TDF/FTC PrEP dosing and pharmacologic sampling

Enrollment will continue until 54 for non-pregnant evaluable participants (i.e., participant with completed data on dosing and PK samples) are enrolled.

- **Group #1:** “7 doses per week or Perfect Adherence arm”— cisgender women will receive a single tablet of co-formulated 300 mg TDF/ 200mg FTC once daily (7 doses per week).
- **Group #2:** “4 doses per week or Moderate Adherence arm” — cisgender women will receive a single tablet of co-formulated 300 mg TDF/ 200mg FTC tablet on Monday, Tuesday, Thursday, Friday.
- **Group #3:** “2 doses per week or Poor Adherence arm” — cisgender women will receive a single tablet of co-formulated 300 mg TDF/ 200mg FTC tablet on Monday and Tuesday.

Justification for non-daily dosing of PrEP groups:

In this study we propose to randomize cisgender women (non-pregnant cohort) to non-daily dosing of PrEP (2, or 4 doses per week). The non-daily dosing is needed to help investigate and demonstrate dose proportionality of TFV and TFV-DP concentrations. The adherence-concentration thresholds derived from this dosing frequency will help guide clinical decisions on drug levels associated with HIV protection in cisgender women and adherence level required to achieve those concentrations. Only daily PrEP is recommended by WHO and the Kenya national guidelines for protection from vaginal HIV exposure and we have carefully considered the risks associated with non-daily in planning this proposal. As detailed in eligibility section, only non-pregnant cisgender women at low HIV risk based on Kenya guidelines will be enrolled and cisgender women will receive full package of HIV prevention, including risk reduction counseling, condoms and STI treatment at each visit. We will also perform monthly HIV testing.

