5.2.1 Dosing schedule and assessment of compliance

The design of the study is guided by the ~17 day half-life of TFV-DP in DBS, including 8 weeks of dosing to achieve approximately 90% of steady-state, weekly sampling at convenience times (i.e., rather than troughs), and three dosing groups (2, 4, and 7 doses per week) to demonstrate dose-proportionality. All cisgender women will be followed for 8 weeks with DOT PrEP to establish steady state in DBS and WB, and up to 8 weeks for two post-DOT PrEP sampling visits. We have chosen a dosing frequency scheme for non-daily doses to directly replicate the STRAND DOT study schedule based on the ~17 day half-life of TFV-DP in DBS: The 2 doses per week will be taken on Monday and Tuesday, and the 4 doses per week on Monday, Tuesday, Thursday, and Friday. This schedule will permit simultaneous evaluation of concentrations derived from intermittent and day-by-day dosing. The operationalization of specific days for dose taking can be adjusted prior to study start while maintaining the randomized adherence patterns (frequency of dosing taking) to permit efficient study operations and to minimize the burden on study participants. This is possible due to TFV-DP long half-life and planned sampling at steady state. Therefore, any chosen days would still be appropriate.

All doses will be witnessed, as described above, in person by a study personnel in private room at the Thika clinic or other predetermined location to maximize convenience for the participant. On dosing visits, the participant will take the dose by mouth and study personnel will ensure the tablet is swallowed by

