7.3.2 Secondary outcomes

1. Examine models to predict non-daily adherence based on TFV/FTC and TFV-DP in DBS.

We assume the modeling approaches of Aim-1. We will first consider a saturated model allowing a separate mean for each dose/adherence group. The results will then be compared to a reduced model with a class variable indicating non-daily dosing groups” or 100% dosing (that is, the effect of “non-daily dosing” adherence does not differ by dose groups). Drug concentration predictors of “non-daily dosing” will focus on TFV-DP in relationship to other drug moieties such as FTC-TP and FTC and TFV. For instance, the ratio of TFV-DP to FTC-TP may be used as a predictor of “2” versus “4 dosing per week. A proportional odds logistic approach which allows for an ordinal outcome and extensions which control for correlations between repeated measurements on a subject will be utilized in SAS or R statistical software. In addition, we will employ PK models (see Aim-1) to simulate TFV-DP to FTC-TP ratios for other dose regimens and estimate cut points for predicting non-daily dosing patterns.

2. To quantify the effect of pregnancy on the benchmark concentrations of TFV, TFV-DP, FTC, and FTC-TP in pregnant cisgender women using daily DOT FTC-TDF PrEP.

Using modeling approaches, we will compare the benchmark concentrations of TFV, FTC, TFV-DP, and FTC-TP between pregnant cisgender women using daily DOT FTC-TDF PrEP. Analyses will be stratified by age and pregnancy gestation.

3. Examine relationships among drug concentrations in plasma, RBC, DBS, and PBMC.

We will use mixed and non-linear mixed effects models to determine if concentrations in various matrices are related.

4. Evaluate the influence of demographics, biological) on drug concentrations.

Kruskal-Wallis parametric test will be used to compare demographics and key study variables (e.g., age, pregnancy, mean corpuscular volume and HCT, contraception use, study arm, BMI, eGFR). Secondary analyses are considered hypothesis generating and will not correct for multiple comparisons.

5. Compare drug concentrations in DBS from fingerstick versus transferring blood from blood tubes.

Since these are paired DBS samples, we will compute the ratio of TFV-DP in the two samples and a mixed model on the natural log of the ratio will be utilized to determine if CI is within 0.8 and 1.25, indicating equivalence. Bland-Altman analyses will also be evaluated.

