7.5 Randomization and Blinding Procedures

The study design for non-pregnant cohort will be an open-label, randomized study with three arms. The randomization assignments cohort will be made at enrollment if the participant is eligible and agrees to enroll. Randomization will be according to the PrEP dosing frequency and vaginal tissue collection plan (either sampling day 4 or day 7) 1:1:1 fashion programmed by the study statistician and generated from REDcap. Randomization will be done at enrollment.

The allocation of participants for the 3 study arms will be the following:

	2 doses per week	4 doses per week	7 doses per week	Total
Total	18	18	18	54

The study design for the pregnant cohort will be an open-label, non-randomized study with only DOT PrEP daily dosing regimen (7 doses per week).

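### Secondary outcome 1 adds a repeated-measures term to a dosing-frequency outcome that never changes within a woman, so the most natural fits (random intercept, exchangeable GEE) are unusable

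*Combined protocol and SAP*

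**What the plan says.** Section 7.3.2, item 1, sets out models to predict non-daily dosing from drug levels. Concentrations are the predictors and dosing frequency is the outcome: "the ratio of TFV-DP to FTC-TP may be used as a predictor of" 2 versus 4 doses per week. The method is "A proportional odds logistic approach which allows for an ordinal outcome", to which the plan adds that "extensions which control for correlations between repeated measurements on a subject will be utilized in SAS or R statistical software". It does not name the extension, the visits that enter, or the unit of analysis. The item opens by carrying over the Aim 1 modelling approaches, which in Section 7.3.1 include a random subject effect.

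The design sections fix the outcome for each woman. Under Section 2.5.1 non-pregnant women "will be randomly assigned to 1 of 3 dosing frequencies of DOT TDF/FTC PrEP". Section 7.5 says "The study design for non-pregnant cohort will be an open-label, randomized study with three arms" and "Randomization will be done at enrollment". Section 5.2.1 describes a single dosing period: "All cisgender women will be followed for 8 weeks with DOT PrEP to establish steady state in DBS and WB". The pregnant cohort takes daily doses only (Section 2.6).

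**The concern.** A correlation extension is needed when the outcome varies within a subject and those values are correlated. Here the outcome is the assigned dosing frequency, and only the concentrations repeat. A woman sampled nine times during dosing supplies nine rows with the same outcome value.

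A model that tries to estimate within-woman outcome correlation from such data is pushed to the edge of its parameter space. The subject effect can account for the outcome completely, and little or nothing is left for the concentration. The scientific question is a between-woman one: can a woman on 2 doses be told from a woman on 4? At stake is whether this model gives usable predicted probabilities, and whether a working marker such as the TFV-DP to FTC-TP ratio might be reported as uninformative.

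Section 7.3.1 calls the design an incomplete block, a label for designs in which a subject receives more than one condition. A repeated-measures ordinal model would make sense there. That this is where the wording came from is an inference, but the label does not match the parallel allocation.

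**Working it through.** The plan states no power, sample size or estimate for this model, so there is no figure to reproduce. The check is algebra plus simulation.

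**Inputs from the documents.** 18 women per arm, 54 in all (Sections 7.4, 7.5). Nine samples per woman during dosing: day 4 and weeks 1 to 8 (Sections 5.2.2, 9.1). TFV-DP CV 25.2% (Section 7.4), which gives a between-woman log SD of √ln(1 + 0.252²) = 0.25. Half-life 17 days (Section 5.2.1).

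**Assumptions.** Log concentration = log(dose) + woman effect + visit noise. The documents give no within-woman SD, so 0.15 to 0.30 on the log scale was used. A between-woman SD of 0.40 was tried as an alternative. The documents give no variability for the TFV-DP to FTC-TP ratio, so a single log concentration stands in for it.

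**Step 1: random-intercept proportional odds.** The model is logit P(Y ≤ c) = θ_c − βx_ij − b_i, with b_i ~ N(0, σ²). Put γ = β/σ and τ_c = θ_c/σ. As σ grows without limit, the likelihood contribution of a woman tends to:

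- lowest category: Φ(τ₁ − max γx)
- middle category: Φ(τ₂ − max γx) − Φ(τ₁ − min γx)
- top category: 1 − Φ(τ₂ − min γx)

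The maximum and minimum are over her own visits. Visit-to-visit spread in x therefore penalizes any non-zero slope. With γ = 0 the limit is the intercept-only model with one row per woman: −2logL = 2 × 54 × ln 3 = 118.7.

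One simulated data set, between/within SD 0.25/0.25, plateau samples:

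| σ | −2logL | β/σ | LR for predictor |
|---|---|---|---|
| 2 | 275.9 | 3.23 | 128.0 |
| 5 | 183.3 | 1.33 | 41.8 |
| 10 | 148.5 | 0.74 | 18.8 |
| 20 | 132.6 | 0.41 | 9.0 |
| 40 | 125.3 | 0.22 | 4.4 |
| limit | 118.7 | 0 | 0 |

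The fit keeps improving as σ rises, so there is no finite estimate, and the end point is the model with no predictor. One week-8 row per woman on the same data gives LR 62.0.

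**Step 2: the limit over 100 replicates per setting.**

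| SD between/within, visits | Limit LR, median (share significant) | One week-8 row, median LR (share significant) |
|---|---|---|
| 0.25/0.15, plateau | 13.6 (97%) | 75.9 (100%) |
| 0.25/0.25, plateau | 0 (0%) | 61.8 (100%) |
| 0.25/0.15, day 4 to week 8, no adjustment for accumulation | 0 (0%) | 75.9 (100%) |
| 0.40/0.30, plateau | 0 (0%) | 40.8 (100%) |

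**Step 3: GEE, 2 versus 4 doses, 200 replicates.** An exchangeable working correlation ρ over m rows weights within-woman contrasts relative to the woman's mean by (1 + (m − 1)ρ)/(1 − ρ). The fitted ρ was about 0.995. With m = 9 the ratio is (1 + 8 × 0.995)/0.005 = 1,792. Because the outcome has no within-woman variation, the slope is forced towards zero.

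| SD between/within | Exchangeable: slope (robust z) | Independence, robust SE: slope (robust z) |
|---|---|---|
| 0.25/0.15 | 0.022 (7.0) | 9.25 (4.8) |
| 0.40/0.30 | 0.006 (4.8) | 2.93 (4.0) |

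On the probability scale, the typical 2-dose and 4-dose women lie ± ln 2/2 = ± 0.347 from the midpoint. With slope 9.25 the log-odds are ± 3.21 and the fitted probabilities of 4 doses are 0.04 and 0.96. With slope 0.022 the log-odds are ± 0.008 and the probabilities are 0.498 and 0.502.

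**The case against.** The strongest reply is that the plan names no failing model. It speaks only of extensions, and a marginal model with independence working correlation and cluster-robust standard errors is one. That method works (Step 3). This stands: a reader might infer that the analysis must fail as written, and the documents do not support that. But the item carries over the Aim 1 approach, whose mixed model has a random subject effect, so the natural reading is one that fails. The plan gives no pointer to the version that works.

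A reader might also infer that real predictors will always look useless. They will not. With low visit noise at plateau the random-intercept limit kept significance in 97% of replicates, although the statistic fell from 75.9 to 13.6. The exchangeable GEE kept a large z; what it loses is a meaningful slope and usable probabilities.

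Nor can it be said that cut points for non-daily dosing become unobtainable. Item 1 goes on to derive them from PK simulation, and Section 7.3.1 obtains concentration thresholds from linear mixed models, 25th percentiles and ROC curves. Neither route needs the ordinal repeated-measures fit.

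Two further points are fair. The analysis is secondary and declared exploratory. The breakdown would probably be noticed at fitting, but the replacement would then be chosen with the data in hand.

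One exception to a fixed frequency exists: a woman who becomes pregnant may stop or move to daily dosing (Section 8.5). That is too rare to identify a within-woman correlation.

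**Conclusion.** The concern holds in a limited form. The outcome in secondary outcome 1 is constant within each woman, so there is no within-woman outcome correlation to model. A random-intercept ordinal model has no finite variance estimate and lost the predictor entirely in three of the four settings tried. An exchangeable GEE gives a correlation near 1 and a slope near 0, hence uninformative predicted probabilities, even when its test statistic is large. Independence working correlation with cluster-robust standard errors does not fail.

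That the outcome never varies follows from the design and needs no assumption. The sizes depend on the assumed within-woman SDs and on log concentration standing in for the ratio. Reading the ordinal outcome as assigned dosing frequency is an inference from the 2-versus-4 example, but no other ordinal outcome fits the item.

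The damage is confined to one exploratory model; the dose-proportionality and threshold analyses in Section 7.3.1 do not rest on it. It is worth correcting before analysis because the repair is cheap and needs no new data.

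**What to change.** In Section 7.3.2, item 1, state the outcome (assigned dosing frequency), the unit (the woman) and the visits used. Then specify one of these:

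- **Simplest:** proportional odds with one steady-state value per woman (N = 54), either week 8 or the mean of weeks 6 to 8, and no within-subject term. Choose in advance: with a 17-day half-life, week 6 is at 1 − 2^(−42/17) = 82% of plateau and week 8 at 1 − 2^(−56/17) = 90%.
- **All samples, same direction:** independence working correlation with cluster-robust standard errors.
- **All samples, reversed:** log concentration or log ratio as outcome, arm and week as fixed effects, woman as random effect. Derive class probabilities and cut points from the fitted arm distributions.

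In each case validate by leaving out whole women, not single samples. Pre-specify a penalized fit for the logistic versions, because near-separation of the 2- and 4-dose arms is likely at 18 per arm with a CV near 25%. Correct the incomplete-block label in Section 7.3.1.

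The cost is SAP wording and minor programming. The one-row version uses fewer samples per woman, but the outcome holds only 54 independent values however many rows are entered.

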1.2.3 Pharmacokinetic TDF/FTC PrEP Adherence in Pregnancy

[figure not shown]
Work we have done recently suggest that TFV and TFV-DP concentrations may be lower in pregnant than non-pregnant periods⁵²; concentrations adjusted for adherence were 45%-58% lower during pregnancy, with the reduction more pronounced in the 3rd trimester (**Figure 2**). Indeed, our pregnancy results have now been replicated by recent IMPAACT 2009⁵⁶, a PK study among 40 16-24 years old HIV-

uninfected pregnant and postpartum women and their infants (n=20 singleton pregnancy at 14-24 weeks' gestation and n=20 postpartum within 6-12 weeks after delivery) to establish the plasma and DBS drug concentrations associated with daily directly observed oral TDF/FTC PrEP during pregnancy and postpartum conducted in Uganda, Zimbabwe, and South Africa. These data showed that DBS TFV-DP level in pregnant women were nearly 30-40% lower than in postpartum women⁵⁶. However, IMPAACT 2009 study did not measure levels in PBMCs needed to link cumulative dosing thresholds and TFV-DP concentrations with PrEP efficacy in cisgender women. Thus, the proposed is complementary and will provide new data on drug levels in PBMC to address this knowledge gap. Changes in pregnancy may include: 1) increased gastrointestinal transit time that can alter the rate and extent of drug absorption; 2) changes in total body water and fat, increasing drug distribution volume; and 3) increased renal elimination. These results, as well as evidence that women may require higher adherence levels for similar PrEP efficacy than MSM because of lower active drug concentrations in genital versus rectal compartments⁵⁷, warrant controlled studies with DOT PrEP in pregnant women.

Experience with DOT PK study of TDF/FTC PrEP in African cisgender women: We have strong field

experience in conducting intensive PK^{58, 59} and antiviral medication studies in Africa^{9, 50, 60-62}, including in understudied populations⁵⁸. We conducted the only PK study of maternal and infant exposure to TDF/FTC PrEP via breastmilk in Uganda and Kenya (ClinicalTrials.gov: [NCT02776748](https://clinicaltrials.gov/ct2/show/study/NCT02776748))⁵⁸, achieving 100% retention and demonstrating limited breast milk excretion and low infant absorption. The data from that study directly informed WHO guidelines on the use of PrEP in breastfeeding (**Figure 3**)^{58, 63}. We will utilize our experience from this study to refine our approach in this proposal.

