2.4 Secondary Objectives

- 1) To define the expected concentrations and dose-proportionality for TFV-DP in PBMC and vaginal tissue
- 2) To quantify the effect of pregnancy on the benchmark concentrations of TFV, TFV-DP, FTC, and FTC-TP in pregnant cisgender women using daily DOT FTC-TDF PrEP
- 3) Examine relationships among drug concentrations in plasma, WB, DBS, and PBMC.
- 4) To determine the influence of biological variables (e.g. mean corpuscular volume and HCT, age, weight, sex, metabolites from metabolomics, and genetic variability in drug transporter/clearance proteins) on drug concentrations.
- 5) Compare drug concentrations in DBS from fingerstick versus transferring blood from blood tubes.

[figure not shown]

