2.5.2 Study design for pregnant cisgender women

This will be an open-label, non-randomized, single-arm, pharmacologic study of daily directly observed therapy. In addition to the cohort of non-pregnant cisgender women describe above, a contemporaneous cohort of up to 18 pregnant cisgender women will be recruited to evaluate the impact of pregnancy on blood and cellular drug benchmark concentrations. Cisgender women must be at 13-26 weeks gestation to give sufficient time for 8 weeks of DOT follow-up. This gestation age was chosen to balance feasibility and risk-benefit and is informed by preliminary work we have done that shows greater reduction in TFV and TFV-DP concentrations in the 2nd and 3rd trimester’s compared to the 1st trimester⁵². We will make all effort to have cisgender women across the entirety of this gestation age spectrum to allow analyses that look across the 2nd and 3rd trimester. To ensure an ethical approach for provision of PrEP in pregnancy (i.e., only exposing PrEP to those who want and might benefit from it) all pregnant cisgender women will be at high risk for HIV and willing to use PrEP. HIV risk and eligibility will be determined according to the Kenya guidelines for PrEP, as described in Table 3. Pregnant cisgender women will receive only daily PrEP dosing (7 doses per week) and matched on age to non-pregnant cisgender women in daily dosing arm. After 8 weeks of DOT PrEP, pregnant cisgender women will be linked to continue PrEP at the clinic of their choice, including at the Thika site clinic itself, permitting seamless access to PrEP and continuation after the study.

Table 3: Kenya national guideline indicators of substantial risk for HIV and indication for PrEP:

Partner of HIV-infected person not on ART or on ART for <6 months
Has >1 partner of unknown status
Engages in transactional sex
History recent STI (past 6 months)
Recurrent PEP use
Inconsistent or no condom use
Injection drug use.

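### Secondary outcome 4 tests influences on drug concentration, including pregnancy, with a rank test that cannot adjust for dose; if the dose arms are pooled, the pregnancy result would be masked, reversed or diluted

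*Combined protocol and SAP*

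**What the plan says.** Item 4 of Section 7.3.2 has this aim: "Evaluate the influence of demographics, biological) on drug concentrations". The method is one sentence: "Kruskal-Wallis parametric test will be used to compare demographics and key study variables". Its examples include pregnancy and study arm, along with age, BMI, eGFR, contraception and the red-cell measures MCV and hematocrit. Study arm is one more entry on the list. Nothing says that the other comparisons are stratified by arm, adjusted for dose or restricted to one arm.

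Pregnancy also has its own analysis. Item 2 of the same section says "we will compare the benchmark concentrations of TFV, FTC, TFV-DP, and FTC-TP between pregnant cisgender women using daily DOT FTC-TDF PrEP", and then "Analyses will be stratified by age and pregnancy gestation". The first sentence gives one side of a comparison and not the other. Section 2.5.2 supplies the likely counterpart: "Pregnant cisgender women will receive only daily PrEP dosing (7 doses per week) and matched on age to non-pregnant cisgender women in daily dosing arm".

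Three other places bear on the point. Section 7.3.1 treats steady-state concentration as proportional to dosing frequency and expects to analyse it on the log scale. Primary outcome 2 in that section adjusts its models for study arm, age, contraception, BMI, eGFR and hematocrit. Section 7.3.2 labels the secondary analyses as exploratory, without multiplicity correction.

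**The concern.** By the plan's own pharmacology, dosing frequency is the main driver of concentration, and it varies 3.5-fold (7/2) across the randomised arms. A one-factor rank test has no place for it.

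For pregnancy the omission can bias the result, because dose and pregnancy are linked by design: all pregnant women are on the highest frequency, and two thirds of the non-pregnant women are on lower ones. The expected effect of pregnancy (lower levels) and the effect of the dose imbalance (higher levels in the pregnant group) act in opposite directions.

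For age, MCV, hematocrit, BMI and eGFR there are two smaller costs. Dose variation sits in the error, and continuous measurements must be cut into groups for which no cut-points are given.

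At stake is a reported pregnancy result that could contradict the one from item 2, with no rule for which prevails, and covariate tests with little power.

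**Working it through.** **Plan's own figures.** The plan gives no power or detectable difference for these tests, so there is none to reproduce. Section 7.4 gives a precision target for a single mean only. Its variability figure does reproduce: 405/1605 = 0.252.

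**Inputs**
- Group sizes: 18 per dose arm (54 non-pregnant) and 18 pregnant (Section 7.4).
- Concentration proportional to doses per week (Section 7.3.1), so the arms sit at 2/7, 4/7 and 1 of the daily level.
- CV 25.2% for DBS TFV-DP (Section 7.4). Log SD = √ln(1 + 0.252²) = 0.248. CVs of 40% and 60% are assumed as a range.
- Pregnancy effect (Section 1.2.3): "concentrations adjusted for adherence were 45%-58% lower during pregnancy". The same section cites a reduction of 30-40%, against postpartum women.
- Two-sided 0.05, assumed, since the plan gives no level.

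**Pooled comparator.** Geometric mean of 2, 4 and 7 = (2 × 4 × 7)^(1/3) = 3.83 doses a week, and 3.83/7 = 0.547 of the daily level. The arithmetic version is (13/3)/7 = 0.619. A reduction r puts pregnant women at (1 − r), so the expected pooled geometric ratio is (1 − r)/0.547.

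**Simulation.** Log-normal data, Kruskal-Wallis, 18 pregnant against all 54 or against the 18 in the daily arm, at CV 25.2%:

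| True reduction | Pooled ratio | Pooled test significant | Direction when significant | Daily arm only, significant |
|---|---|---|---|---|
| 0% | 1.83 | about 100% | falsely higher | about 5% |
| 30% | 1.28 | about 22% | wrong | 98% |
| 35% | 1.19 | about 4% | wrong | about 100% |
| 40% | 1.10 | 0.2% | wrong | about 100% |
| 45% | 1.006 | about 0.01% | none to speak of | about 100% |
| 58% | 0.77 | about 41% | right | about 100% |

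Separate runs ranged over 22-24% at a 30% reduction, 3-4% at 35% and 41-43% at 58%. At 35% the pregnant median is the higher one in about 92-93% of trials, although few of these are significant.

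**Sensitivity.** At a 45% reduction the pooled test rejects in 0.5% of trials at CV 40% and 1.6% at CV 60%. The daily-arm comparison rejects in 99% and 87%. Replacing strict proportionality by the 350, 700 and 1,250 fmol/punch benchmarks of Section 1.2.1 gives a pooled level of 0.539. Rejection is then 27% (wrong direction) at a 30% reduction, 0.01% at 45% and 31% at 58%.

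**Other covariates within the 54.** The variance of ln(2), ln(4), ln(7) is 0.512² = 0.263. Ignoring dose raises the log variance from 0.062 to 0.062 + 0.263 = 0.324 (unrounded inputs), a factor of 5.3. For a two-level covariate split 27/27, a 20% decrease is detected with about 26% power by Kruskal-Wallis and 90% with ln(dose) in a linear model. For a 20% increase the figures are 19% and 74%. Because dose is randomised, a covariate unrelated to it is not biased by the omission.

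**The case against.** The strongest reply is that item 4 is not where the plan answers the pregnancy question. A reader might infer from the table that the trial would miss or reverse the pregnancy effect in its overall hypothesis. The documents do not support that. Item 2 is a separate modelled analysis of women on daily dosing, and Section 2.5.2 matches the pregnant cohort to the daily arm, so the sound comparator can be identified from the design. This stands. What remains is that item 2 does not name that comparator.

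Second, pooling is an inference. It is the natural reading of a one-factor test run over the list, all the more because primary outcome 2 states adjustment for study arm and item 4 does not. But it is not written down, so the pregnancy figures hold only on that condition.

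Third, a reader might infer that the pregnancy effect always cancels. Near-exact cancellation is specific to a reduction of about 45%. Smaller effects tend to reverse, mostly without reaching significance, and a 58% reduction is only diluted.

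Fourth, primary outcome 2 already adjusts most of the listed covariates for study arm. That is a partial answer: those models serve to set thresholds, and their adjustment list omits MCV and pregnancy.

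The exploratory label covers multiplicity; it does not remove confounding by dose.

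Some neighbouring complaints should not be pressed. Calling the test parametric is a slip of wording. Sex appears only as an example in the objectives ("age, weight, sex, metabolites from metabolomics") and not in item 4. Stratifying by gestation is not contradictory, since each gestational stratum can be compared with the same daily arm. The number of strata is not given, so no cell size can be asserted.

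**Conclusion.** The point holds in a limited form. Item 4 names a test that cannot adjust for the main determinant of its outcome, and it puts pregnancy, which is tied to dose by design, on the list of factors.

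If the arms are pooled, the pregnancy result from item 4 is uninformative or misleading over the whole 30-58% range that the protocol cites: power is about 0% at 45% and about 41% at 58%, the direction tends to be wrong at 30-35%, and there is a near-certain false increase if pregnancy has no effect. The same 18 pregnant women compared with the daily arm alone would give 98% power or more over that range at CV 25.2%. For other covariates the loss is efficiency only, from about a 5-fold larger log variance.

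These figures rest on dose-proportionality, log-normal concentrations, a DBS CV taken from US men, full groups of 18 and an assumed two-sided 0.05. The cancellation near 45% persists at CVs of 40% and 60%. The finding concerns an exploratory analysis and does not undermine the design or the modelled pregnancy comparison in item 2.

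**What to change.** In item 4 of Section 7.3.2:
- Replace Kruskal-Wallis by a linear model of ln concentration on ln(dose) or study arm plus the covariate, as a mixed model where repeated samples are used. Keep age, MCV, hematocrit, BMI and eGFR continuous.
- Estimate pregnancy as a geometric mean ratio with its confidence interval against the non-pregnant 7-dose arm only, adjusted for age. Restricting to that arm means the estimate does not depend on dose-proportionality holding.

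In item 2:
- Name the non-pregnant 7-dose arm as the comparator, and say that gestation is examined within the pregnant women.

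The cost is SAP wording and reliance on a log-normal model, which Section 7.3.1 already expects to use. No visit, sample or sample size changes.
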